Cutaneous manifestations of COVID-19 were first reported in early 2020 in China with only 2 out of 1,099 positive cases (13). However, a study carried out later in Italy found that 18 out of 88 COVID-19 positive patients developed dermatological alterations, of which 8 developed cutaneous involvement at the onset and 10 after the hospitalization. Cutaneous manifestations included erythematous rash (14 patients), widespread urticarial (3 patients) and chickenpox-like vesicles (1 patient) (14). Since then, several studies have discussed reports of patients infected with COVID-19 associated with vesicular manifestations of Herpes Zoster (HZ) (15, 16, 17, 18). A recent Turkish publication collecting data from fifteen tertiary hospitals from 13 provinces described an increase in the number of HZ diagnoses when comparing two months periods pre and post onset of the pandemic (19). These results are consistent with a latter study carried out in Brazil in which the number of HZ cases were quantified during the months of March to August from 2017 to 2019 and compared with the similar period in 2020 (20). Although the HZ cases were not assessed within COVID-19 positive patients, an extra 10.7 cases per million inhabitants during the pandemic was reported, which might suggest a correlation between both diseases.

HZ is a severe disease resulting from the reactivation of Varicella Zoster Virus (VZV), which remains latent in sensory nerve ganglia after primary infection (Varicella) (21). HZ can result in dermatomal chronic pain which is its most common complication (post-herpetic neuralgia, PHN) (22). Many patients with PHN go on to develop severe physical, occupational, and societal disabilities because of the enduring pain. Both, HZ and PHN result in reduced quality of life as well as individual and societal health care costs (23).

VZV reactivation seems to be a result of a waning of VZV-specific cell-mediated immunity as occurs with ageing or in subjects with immunosuppressive disorders (24). SARS-CoV-2 infection is associated with lymphopenia with reduced numbers of CD4 + and CD8 + T cells, B cells and natural killer (NK) cells (25). Because cell-mediated immunity is key in the protection against HZ (26), lymphopenia could predispose COVID-19 patients to HZ development. However, more scientific evidence needs to be provided to corroborate this hypothesis.

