4.6 Covariates

Covariate information will be collected on sociodemographic, spatial information, vaccination against Sars-Cov-2 and comorbidities. The source of the eHR databases and the variables needed to create the covariates is given in Annex 1.

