4.6.3 Comorbidities

Comorbidities that have been identified as risk indicators for HZ will be considered for the analysis. These conditions will be identified by systematic search of ICD-codes in the hospital or ambulatory databases, MBDS or SIA. Subjects will be considered to

Disease classification	ICD-10
Diabetes	E10-E14
COPD	J44
Ischemic heart disease	120-125
Other heart disease	127-152
Kidney disease	N18-N19
Immunocompromised	
HIV	B20-B24
Cancer	C00-D49
TOTS	Z94
IBD	K50-K51
RA	M05-M14
SLE	M32

have a given condition from the first appearance of the comorbidity-related diagnosis date until the end of the follow-up period.

COPD: chronic obstructive pulmonary disease, HIV: human immunodeficiency virus, TOTS: Transplanted organ and tissue status, IBD: inflammatory bowel disease, RA: rheumatoid arthritis, SLE: systemic lupus erythematous.

Presence of any comorbidity.

This is a binary variable indicating whether the patient has at least one comorbidity defined above.

Number of underlying conditions

This is a categorical variable indicating the number of comorbidities (0, 1, 2, 3+).

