Abucasis SIA-GAIA (Ambulatory Information System - Care provision management) is a primary care database used across the entire Valencia healthcare system that contains medical information for each patient attended in the Primary Care (PC) setting (General Practitioners, GPs, and specialists). It was set up in 2006 and the percentage of the population included increased from 73.1% in 2007 to 88.8% in 2008 and to 95.7% in 2009. This database contains primary care diagnoses (physician coded using the International Classification of Diseases Revision, Clinical Modification (ICD-CM)) and all drug prescriptions (using Anatomical Therapeutic Chemical (ATC) Classification System). In addition, the physician or paediatrician and nurse responsible recorded text about each episode and about the patient is included. The database is also used at Specialty Centres and is considered reliable since 2007.

Hospital Discharge Database

The Spanish hospital discharge database, MBDS (Minimum Basic Data Set), collects diagnosis and procedures as an assessment of medical activity. The coding system used is ICD-9-CM until 2016 and ICD-10-CM afterwards. The main discharge diagnosis is coded in first position, and diagnosis relevance decreases as the position number increases. Using MBDS is compulsory for all public hospitals, and over 95% of all discharges are included. According to the Spanish Ministry of Health, data are considered reliable since 2002.

Microbiological Surveillance Network

The Microbiological Surveillance Network (RedMIVA) contains all the results (positive or negative) given by all the microbiology laboratories of the Valencian Public System network. All data is transferred from the laboratories to the RedMIVA database on a daily basis. Data are considered reliable since 2008.

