4.9.6 Primary objective

To develop the primary objective, we will compare the incidence of HZ among SARS-Cov-2 free and Sars-Cov-2 laboratory-confirmed subjects 50 years and older during the pandemic period. For this purpose, models using individual patient data or grouped will be implemented.

[figure not shown]

Figure 4: Cohort diagram for HZ rates comparison among subjects with and without previous episode of COVID19

The risk of HZ in subjects with Sars-cov-2 respect to subjects without Sars-Cov-2 will be estimated by a multivariate Poisson or negative binomial model according to applicability assumptions. Individual data will be grouped by SARS-Cov-2 free and Sars-Cov-2 laboratory-confirmed exposure, age, sex and comorbidities. Individual and grouped data can both be analyzed with the Poisson (or Negative binomial) distribution. Given the usual large size of the cohort, estimation when using grouped data is considerably quicker than when using individual level data and the results for both approaches are remarkably similar.

The number of HZ cases by aggregation unit will be compared among SARS-Cov-2 free and labconfirmed subjects. Age, sex, and comorbidities will be considered for the adjustment, and the person-time-at-risk (in years) as an offset term. RR and their 95% confidence or credible intervals will be reported.

Besides, individual-level risk of HZ between SARS-Cov-2 free vs lab-confirmed will be estimated by Cox regression model for right censored data. The abovementioned variables will be also considered for the adjustment.

Both approaches will be performed and compared for the robustness of the results.

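### Immune status is adjusted for by diagnosis codes alone and no prescription data are requested, leaving residual confounding by prior immunosuppressive treatment whose size and direction the protocol does not give

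*Protocol*

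**What the plan says.** - **Mechanism.** Protocol section 1 attributes reactivation of the virus to "waning of VZV-specific cell-mediated immunity as occurs with ageing or in subjects with immunosuppressive disorders".
- **Adjustment.** For the Poisson or negative binomial model, 4.9.6 states "Age, sex, and comorbidities will be considered for the adjustment". For the Cox model it adds "The abovementioned variables will be also considered for the adjustment".
- **Covariates.** Section 4.6 opens: "Covariate information will be collected on sociodemographic, spatial information, vaccination against Sars-Cov-2 and comorbidities". Temporal variables follow in 4.6.4. No drug variable is listed.
- **Immune status.** Section 4.6.3 groups HIV, cancer, transplant, IBD, RA and SLE as immunocompromised and lists COPD separately. It says: "These conditions will be identified by systematic search of ICD-codes in the hospital or ambulatory databases, MBDS or SIA".
- **Availability.** Section 4.7.1 lists Abucasis SIA-GAIA among the registries to be used and says it contains "all drug prescriptions (using Anatomical Therapeutic Chemical (ATC) Classification System". Section 1 adds that medication data can be linked at individual level.
- **Extraction.** From SIA, Annex 1 requests diagnosis and visit fields only. In its variable table the single SIA-GAIA row holds just the subject identifier. Section 4.12 admits SIA, CMBD and RedMIVA data within the SIP population and does not name GAIA.

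**The concern.** If HZ follows a fall in cell-mediated immunity, drugs that lower that immunity are candidate confounders on the protocol's own reasoning. A diagnosis code does not show whether the patient was treated. A COPD patient on repeated oral steroids is grouped with COPD patients who take none. A patient treated for psoriasis or vasculitis, neither of which is listed, is grouped with untreated people.

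If treatment before infection differs between confirmed and free person-time, or between severe and mild cases, part of any HZ difference may belong to that treatment. The study is designed around a 10% difference, so a bias of a few percent counts. A larger sample does not remove it. Comparing the Poisson and Cox results cannot show it either, because both models omit the same variable.

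The gap cannot be left to the statistical analysis plan: the protocol fixes the extraction, and no plan can adjust for data that were never requested.

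**Working it through.** **1. The plan's own figure.** Section 4.9.5 gives 110,000 confirmed and 2,000,000 free subjects, 7 HZ cases per 1,000 person-years in the free group, RR 1.1, alpha 0.05 and power 0.760864. Assume one person-year each.
- Expected events: 110,000 × 0.007 × 1.1 = 847, and 2,000,000 × 0.007 = 14,000.
- Pooled rate: 14,847 / 2,110,000 = 0.0070365.
- Null SE: √[0.0070365 × (1/110,000 + 1/2,000,000)] = 0.0002598.
- SE under the alternative: √(0.0077/110,000 + 0.007/2,000,000) = 0.0002711.
- Two-sided power: Φ[(0.0007 − 1.96 × 0.0002598)/0.0002711] = 0.759.

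The stated power reproduces, and this point does not dispute it.

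**2. Bias factor.** Let p1 and p0 be the share of drug users in the two groups compared, and R the HZ rate ratio for use. Then B = [1 + p1(R − 1)] / [1 + p0(R − 1)]. **The documents give none of these inputs; all are assumed.** B is the bias before adjustment for diagnoses.

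| Contrast (p1 vs p0) | R = 1.5 | R = 2 | R = 3 |
|---|---|---|---|
| Confirmed vs free, 7.5% vs 5% | 1.0375/1.025 = 1.012 | 1.075/1.05 = 1.024 | 1.15/1.10 = 1.045 |
| Severe vs mild, 10% vs 4% | 1.05/1.02 = 1.029 | 1.10/1.04 = 1.058 | 1.20/1.08 = 1.111 |
| Confirmed vs free, 5% vs 7.5% (reversed) | 1.025/1.0375 = 0.988 | 1.05/1.075 = 0.977 | 1.10/1.15 = 0.957 |

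Other assumed primary prevalences give a wider range: 3% vs 2% gives 1.005 to 1.019, and 10% vs 5% gives 1.024 to 1.091.

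**3. After diagnosis adjustment.** The documents do not allow the residual to be calculated. As an illustration only, suppose adjustment halves the difference in use, to 6.25% vs 5%. The factors become 1.03125/1.025 = 1.006, 1.0625/1.05 = 1.012 and 1.125/1.10 = 1.023.

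**4. Scale against precision.** With no true effect there are 770 and 14,000 expected events, so SE(log RR) = √(1/770 + 1/14,000) = 0.037. The chance of a significant result is Φ(ln B/0.037 − 1.96) + Φ(−ln B/0.037 − 1.96). For the unadjusted factors 1.012, 1.024 and 1.045 this is about 6%, 10% and 22%, instead of 5%.

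**5. Imbalance needed to produce RR 1.1 alone.** Solve p1 = {1.1[1 + p0(R − 1)] − 1}/(R − 1). From p0 = 5%, use among confirmed subjects would have to be 25.5% (R = 1.5), 15.5% (R = 2) or 10.5% (R = 3).

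**The case against.** The other side makes four fair points.

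- **Nothing is misstated.** Section 4.7.1 describes what the database contains and does not promise to use prescriptions. Section 4.6.3 states a deliberate choice: "Comorbidities that have been identified as risk indicators for HZ will be considered for the analysis". This is true. The point concerns a design choice, not a contradiction.
- **The diagnoses already do much of the work.** COPD, cancer, transplant, IBD, RA, SLE and HIV are all covariates. This stands, and it limits the point to residual confounding.
- **The bias is small against the noise.** At the planned sizes, SE(log RR) under RR 1.1 is √(1/847 + 1/14,000) = 0.035, so the 95% interval is about ±7%. The middle factor, 1.024, is about two-thirds of one SE. If follow-up stopped at the earliest permitted date, precision would be worse, because November and December hold 151,387 of the 288,311 positive tests of 2020 (53%, table in 4.9.4). This also stands, though bias does not shrink with longer follow-up as noise does.
- **The direction is open.** Nothing in the protocol shows that treated patients are confirmed more often. Most tests were negative, and such patients might avoid exposure. This stands; the reversed row in the table shows the consequence.

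A reader might infer that the study cannot separate the effect of infection from that of earlier treatment, or that treatment could by itself explain an RR of 1.1. The documents do not support either reading. The first does not follow from a bias of 1–5% before adjustment. The second needs the strong imbalance shown in step 5. Nor does 4.7.1 establish that every drug is captured: it describes the primary care and specialist system and does not say that drugs dispensed in hospital are included.

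**Conclusion.** The point holds as one of residual confounding. Neither primary model contains a drug term, the immunocompromised group rests on diagnosis codes, and the extraction list rules out later repair, although a named source is said to hold the data. The severity models in 4.9.9 draw on the same covariates and share the gap.

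The size is about 1–5% on the primary RR and 3–11% on the severity contrast. Both ranges rest wholly on assumed prevalences and drug effects, apply before diagnosis adjustment, and could have either sign. That is material against a target RR of 1.1 but does not invalidate the comparison. The severity objective is secondary and descriptive, so its larger figure carries less weight than the same figure would on the primary result. The change is worth making because it is cheap before extraction.

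**What to change.** 1. **Extraction.** Add ATC code and prescription date for H02 (systemic corticosteroids), L01 (antineoplastics) and L04 (immunosuppressants), from July 2017, to the SIA-GAIA request in Annex 1. Name GAIA among the sources in 4.12.
2. **Primary Poisson and Cox models.** Add a yes/no covariate defined identically for both groups: any such prescription in the 6 months before a common baseline, 14 March 2020 or entry if later. Do not update it over free time while freezing it at the positive sample, since that would measure it differently by exposure group.
3. **Severity models.** These include only confirmed subjects, so use the 6 months before the positive sample. Treatment given for COVID-19 is then not adjusted for.
4. **Sensitivity analysis.** The 6-month window is a convention, and a yes/no term merges one short course with long-term use. Repeat with other windows, or with short use split from repeated use.
5. **Limitations (4.10).** State that drugs dispensed in hospital may be missed and that severity results include the effect of hospital treatment.

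The cost is one more data table under the existing approval route, with no new subjects or procedures. Annex 1 needs revision anyway, because its stated extraction period (2007 to 2015) does not match 4.8. Two weaknesses remain: capture of hospital-dispensed drugs is incomplete, and a fixed baseline misses treatment started after it.

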4.4 Sars-Cov-2 exposure

Exposure status of everyone might change within the follow up period (Figure 3): Sars-Cov-2 unexposed in the pre-pandemic period and Sars-Cov-2 exposed in the pandemic period. Sars-Cov-2 exposure levels will be treated as a time-varying variable and the following states will be considered:

- 1) **Sars-Cov-2 unexposed**: subject's follow up period from the start of follow-up to the declaration of the pandemic in Spain (March 14th 2020).
- 2) **Sars-Cov-2 exposed**: subject's follow up period from the start of the pandemic. We will consider the following 2 comparison groups:
 - **Sars-Cov-2 free**: time from the start of pandemic (or the follow-up) to the date of the first Sars-Cov-2 confirmation (by PCR or Ag test). If no Sars-Cov-2 positive test registered, the time period will be until the end of follow-up.
 - **Sars-Cov-2 laboratory-confirmed**: time from the date of the SARS-CoV-2 positive result in RedMiva to the end of follow up.

[figure not shown]

Figure 3. Example of exposure, follow-up and comparisons in the study.

* Subjects with recurrent episodes of Sars-Cov-2 will be treated separately. If the sample size is not large enough for the analysis, these individuals will be excluded for the analysis.

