4.5 Other health outcomes

4.5.1 Pandemic and pre-pandemic periods

- Pre-pandemic period will be considered from January 1st 2018 to March 14th 2020
- Pandemic period will be considered from March 14th 2020 to the end of study period

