4.6.4 Temporal variables

Temporal variables such as calendar week, month and year will be contemplated to detect trends.

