4.9.8 HZ incidence rates (Descriptive analysis)

[figure not shown]
Incidence rates (number of patients with an incident case of HZ per 1000 persons-years) will be obtained for subjects with and without Sars-Cov-2 in the pandemic period by sex, age-group and comorbidity. HZ incident rates for the pre-pandemic period will be also described by sex, age-group and comorbidity.

The person-time-at-risk (in days) ends at the date of the first event of HZ or the end of follow-up, whichever comes first. Follow-up time will be split according to the time-varying covariates (calendar year, month, week, age and comorbidities). Persons-years will be calculated as the sum of total person-time-at-risk divided by 365.25. Rates 95% confidence intervals will be calculated by the Exact Poisson method.

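### The primary Poisson comparison leaves out calendar time, although confirmed and infection-free person-time fall in different parts of the pandemic period

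*Protocol*

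**What the plan says.** Protocol section 4.9.6 plans a Poisson or negative binomial model on grouped data and names the cells: "Individual data will be grouped by SARS-Cov-2 free and Sars-Cov-2 laboratory-confirmed exposure, age, sex and comorbidities". The adjustment set is the same: "Age, sex, and comorbidities will be considered for the adjustment, and the person-time-at-risk (in years) as an offset term". A second, individual-level analysis "will be estimated by Cox regression model for right censored data", and for it "The abovementioned variables will be also considered for the adjustment". No time axis is given for the Cox model. The two analyses are to be compared as a check of robustness.

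The exposure states are in section 4.4. Free time is "time from the start of pandemic (or the follow-up) to the date of the first Sars-Cov-2 confirmation", or to the end of follow-up if there is no positive test. Confirmed time begins at the positive result. Section 4.5.1 sets the window: "Pandemic period will be considered from March 14th 2020 to the end of study period". Section 4.2 gives 31 December 2020 as the earliest end date.

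Calendar time appears in two other places. Section 4.6.4 says "Temporal variables such as calendar week, month and year will be contemplated to detect trends". Section 4.9.8, on descriptive rates, says "Follow-up time will be split according to the time-varying covariates (calendar year, month, week, age and comorbidities". Neither carries calendar time into the primary model.

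**The concern.** Nearly everyone contributes free time from 14 March 2020 onward, so that time is spread almost evenly over the pandemic period. Confirmed time builds up only as people test positive, and most positives came in the autumn. Exposure is therefore tied to calendar date by design. If HZ incidence, or the chance that an episode is coded, differed between spring and autumn 2020, a model without calendar time attributes part of that difference to infection. This happens inside the primary contrast and is separate from the pre-pandemic versus pandemic comparison of the secondary objectives.

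At stake is the primary RR. The target effect is small, so a modest bias can be a large part of it.

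**Working it through.** **The plan's own figure.** Section 4.9.5 gives power 0.760864 for RR 1.1, with 7 per 1000 person-years, 110,000 confirmed and 2,000,000 free. With one person-year each, expected events are 110,000 × 0.0077 = 847 and 2,000,000 × 0.007 = 14,000. The standard error of log RR is √(1/847 + 1/14,000) = 0.0354. Since ln 1.1 = 0.0953, z = 2.69, and two-sided power is Φ(2.69 − 1.96) ≈ 0.77. A score test gives 0.759. The figure reproduces, so RR 1.10 is a fair yardstick for the bias.

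**Share of free time in 14 March to 31 May 2020.** The window has 18 + 30 + 31 = 79 days. From 14 March to 31 December there are 293 days. The share is 79/293 = 27.0%, or 27.2 to 27.4% once time after a positive test is removed.

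**Share of confirmed time in the same window.** The monthly positives are from section 4.9.4. As a check that can be done by hand, place each month's positives on the 15th (February's on 14 March) and follow them to 31 December:

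| Month | Positives | Days to 31 Dec | Days in window |
|---|---|---|---|
| Feb | 46 | 293 | 79 |
| Mar | 13,009 | 292 | 78 |
| Apr | 11,215 | 261 | 47 |
| May | 2,709 | 231 | 17 |
| Jun | 976 | 200 | 0 |
| Jul | 4,900 | 170 | 0 |
| Aug | 26,679 | 139 | 0 |
| Sep | 28,181 | 108 | 0 |
| Oct | 49,209 | 78 | 0 |
| Nov | 70,279 | 47 | 0 |
| Dec | 81,108 | 17 | 0 |

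Positives × days sum to 23,665,380 in all and 1,591,494 in the window, a share of 6.7%. Spreading positives evenly within each month gives about 6.5%. Over several placements the range is 6.1 to 6.7%. October to December holds (49,209 + 70,279 + 81,108)/288,311 = 200,596/288,311 = 70% of positives. With even spreading, December alone holds 33% of confirmed time against about 10% of free time.

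**Bias when the true RR is 1.** Let HZ rates in the window differ from the rest of the period by a fraction d, equally in both groups, and be constant elsewhere. The unadjusted RR is

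(1 + d × 0.065) / (1 + d × 0.270).

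| Size of change (assumed) | Fall | Rise |
|---|---|---|
| 10% | 0.9935/0.973 = 1.02 | 1.0065/1.027 = 0.98 |
| 20% | 0.987/0.946 = 1.04 | 1.013/1.054 = 0.96 |
| 30% | 0.9805/0.919 = 1.07 | 1.0195/1.081 = 0.94 |
| 40% | 0.974/0.892 = 1.09 | 1.026/1.108 = 0.93 |

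To reach 1.10 from this source alone, the fall must satisfy 1 − 0.065f = 1.1 − 0.297f, so f = 0.1/0.232 = 43%.

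**False-positive rate.** By 31 December 2020 the 110,000 confirmed would have about 24,400 person-years (mean 0.22 years each). With a 30% fall, that is about 167 confirmed and 10,700 free HZ cases. The standard error of log RR is √(1/167 + 1/10,700) ≈ 0.078. The two-sided 5% test would then reject about 14% of the time. For falls of 10% and 20% the figures are about 6% and 9%.

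**Later end date** (no new positives and no censoring at vaccination assumed). To 31 March 2021 the shares are about 3% against 21%, and a 30% fall gives 1.06. To 31 December 2021 they are about 1% against 12%, and it gives about 1.03.

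**The case against.** *The adjustment list is not closed.* Section 4.9.6 says only that variables will be considered, section 4.6 lists calendar terms among the covariates, and an analysis plan not seen here may add them. This shows that the authors had calendar time in mind. It does not rescue the plan as written: once data are collapsed into the stated cells, calendar time is gone and cannot be adjusted for.

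*No fall in recorded HZ is documented.* This stands. A reader might infer that the RR will be pushed above 1, in favour of the hypothesis. The documents do not support that. The rationale cites reports from Turkey and Brazil of more HZ after the pandemic began, and a rise in the window would push the RR below 1. Those reports compare pandemic with pre-pandemic periods elsewhere, so they do not settle the sign here either.

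*The bias is modest and the shares are not fixed.* Only the gap of about 20 points between the shares passes into the RR, not the whole change. The shares assume the earliest end date and take all-age positive tests (288,311) to stand for people aged 50 and over, although section 4.9.3 counts 219,144 confirmed cases in all ages as of January 2021. All of this stands. A later end shrinks both shares but leaves them unequal.

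*The Cox model.* A reader might infer that it carries the same or a larger bias. That requires the clock to restart at the positive result. Section 4.4 makes exposure time-varying, and section 4.2 gives each person a single start of follow-up, 1 January 2018 for most. On that clock, risk sets are nearly matched on calendar date and little bias remains. The protocol does not state the axis, so no Cox magnitude is claimed.

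**Conclusion.** The point holds for the Poisson or negative binomial primary analysis. As written, that analysis has no protection against calendar-time confounding, although confirmed time is concentrated late and free time is not. The imbalance follows from the exposure definitions and the protocol's own test counts. The resulting bias is conditional: its sign and size depend on a calendar change in HZ incidence or recording that the documents do not quantify. Under the assumptions shown, it is a few percent for changes of 10 to 20% and approaches the target RR of 1.10 only for a fall of about 40%.

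For the Cox model, the finding is only that the time axis is unstated. This matters because the two analyses are meant to check each other, and they could agree or disagree because of that choice alone. The plan should be corrected before analysis. The documents do not show that the primary result must be wrong.

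**What to change.** In section 4.9.6, and in item 1 of section 4.9.9 for adults aged 18 and over, add calendar month (or a spline of calendar week) to the grouping cells and to the Poisson or negative binomial model. A change common to both groups then cancels, and the RR under no effect returns to 1.00. For the Cox model, state calendar date as the time axis, with delayed entry and time-varying exposure, so that a confirmed person is compared with free people at risk on the same date.

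The cost is protocol wording, some additional grouping cells and a small loss of precision. The splits by calendar time are already planned in section 4.9.8, and no new data are needed.
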